3.1.4. Post-treatment Follow-up Period

Subjects who discontinue treatment with the IP in the DBTP or OLP, regardless of reason, will enter the PTFP and may continue or complete the long-term follow-up of 5 years from first dose of IP, or 3 years from last dose (whichever occurs later), under the rollover protocol until the End of Trial (see Section 3.3). Specific assessments and visits to be performed during this period are defined in Table 3, Table of Events. After the unblinding, and after DMC's recommendation:

[figure not shown]
- Subjects who received placebo and have been assessed as per protocol at least up to 48 weeks after the first dose of IP (even if the IP is discontinued before completing 48 weeks of treatment), may stop the PTFP and access the OLP to receive luspatercept, if eligible.
- Subjects who received luspatercept and discontinued the IP in the DBTP or OLP may complete the PTFP and continue or complete the long-term follow-up of 5 years from first dose of IP, or 3 years from last dose (whichever occurs later), to complete the Post-treatment Follow-up Period under the rollover protocol until the End of Trial (see Section 3.3). Note: only the visit at 9 weeks after last dose may be performed in this study before moving to the rollover study.

3.1.5. Committees

The conduct of this trial will be overseen by an independent external Data Monitoring Committee (DMC) and by a steering committee (SC). During the DBTP, the DMC will review unblinded data, while the SC will not have access to unblinded data. Refer to Section 9.10.3 and Section 9.10.4 for additional information. Further details will be provided in the DMC and SC charters.

The study will be conducted in compliance with the International Council for Harmonisation (ICH) of Technical Requirements for Registration of Pharmaceuticals for Human Use/Good Clinical Practice (GCP) and applicable regulatory requirements.

Figure 7: Overall Study Design

EOS: end of study; EOT: end of trial; ICF: informed consent form; IP: investigational product; Q3W: every 3 weeks; SC: Subcutaneous.

[figure not shown]
^a Dose may be titrated up to a maximum of 1.25 mg/kg.

^b Double-blind Treatment Period (DBTP) will end after last subject enrolled has completed 48 weeks of treatment or discontinued earlier, or when the study is unblinded.

^c The study will be unblinded 48 weeks after last subject has received the first dose of IP. At that time, subjects still benefitting from luspatercept treatment as well as subjects who received placebo and have been assessed as per protocol up to 48 weeks after the first dose of IP (even if they have discontinued the IP before completing 48 weeks of treatment), may access the OLP to receive luspatercept for maximum 15 months on the basis of DMC recommendation after unblinded data review, and can continue treatment in the rollover protocol after EOT up to 5 years of Dose 1, or treatment discontinuation, whichever occurs later.

^d Subjects in the DBTP who have discontinued luspatercept before the unblinding will continue the PTFP until the End of Trial (EOT) and may continue the PTFP in the rollover study up to 5 years from first dose of IP, or 3 years from last dose (whichever occurs later), may complete the Post-treatment Follow-up Period under the rollover protocol. Subjects in the DBTP who have discontinued the placebo before the unblinding will continue the PTFP until the unblinding and may access the OLP, after DMC's recommendation.

Figure 8: Subjects Study Periods Flowchart

DBTP: double-blind treatment period; IP: investigational product; OLP: open-label phase; PTFP: post-treatment follow-up period.

3.2. Study Duration for Subjects

Study participation for each individual subject will be approximately 4 weeks in the Screening Period, at least 48 weeks in the DBTP, maximum 15 months in the OLP and 5 years from first dose of IP, or 3 years from last dose (whichever occurs later) in Post-treatment Follow-up Period until the End of Trial (Section 3.3)

End of Treatment for each individual subject is defined as the date of the last IP dose in the DBTP or OLP, whichever occurs later.

End of Study for each individual subject should occur after the study is unblinded (ie, 48 weeks after last subject has received the first dose of IP), and the OLP or the PTFP have been completed, as appropriate, or at the End of Trial as defined in Section 3.3, whichever occurs later.

3.3. End of Trial

The End of Trial is defined as the date all subjects complete the OLP (if allowed to access the OLP as defined in Section 3.1.3), or discontinue earlier, or, the date of receipt of the last data

point from the last subject that is required for primary, secondary, and/or exploratory analysis, as prespecified in the protocol, whichever is the later date.

The Sponsor may end the trial when all key endpoints and objectives of the study have been analyzed, and the availability of a rollover protocol exists into which any subjects remaining on study may be consented and continue to receive access to luspatercept, if not yet commercially available, and/or complete the PTFP.

4. STUDY POPULATION

4.1. Number of Subjects

Approximately 150 subjects diagnosed with non-transfusion dependent β -thalassemia (including Hemoglobin E/ β -thalassemia, excluding Hemoglobin S/ β -thalassemia and Hemoglobin H) will be randomized.

4.2. Inclusion Criteria

Subjects must satisfy the following criteria to be enrolled in the study:

1. Subjects must be ≥ 18 years of age at the time of signing the informed consent document (ICF).
2. Subject must understand and voluntarily sign an ICF prior to any study-related assessments/procedures being conducted.
3. Subject is willing and able to adhere to the study visit schedule (eg, not scheduled to receive hematopoietic stem cell transplantation) and other protocol requirements.
4. Subject must have documented diagnosis of β -thalassemia or hemoglobin E/ β -thalassemia. Concomitant alpha globin mutation and/or duplication are allowed.
5. Subject must be non-transfusion dependent, defined as 0 to 5 units of RBCs received during the 24-week period prior to randomization. Note: 1 unit defined for this entry criterion as approximately 200 to 350 mL of transfused packed RBCs.
6. Subject must not be on a regular transfusion program and must be RBC transfusion-free for at least ≥ 8 weeks prior to randomization
7. Subject must have mean baseline hemoglobin ≤ 10 g/dL, based on a minimum of 2 measurements ≥ 1 week apart within 4 weeks prior to randomization; hemoglobin values within 21 days post-transfusion will be excluded.
8. Subject must have performance status: Eastern Cooperative Oncology Group (ECOG) performance score of 0 to 1.
9. A female of childbearing potential (FCBP) for this study is defined as a female who: 1) has achieved menarche at some point, 2) has not undergone a hysterectomy or bilateral oophorectomy or 3) has not been naturally postmenopausal (amenorrhea following cancer therapy does not rule out childbearing potential) for at least 24 consecutive months (ie, has had menses at any time in the preceding 24 consecutive months). A FCBP participating in the study must:
 - a. Have 2 negative pregnancy tests as verified by the Investigator prior to starting study therapy. She must agree to ongoing pregnancy testing during the study, and after end of study treatment. This applies even if the subject practices true abstinence* from heterosexual contact.
 - b. Either commit to true abstinence* from heterosexual contact (which must be reviewed on a monthly basis and source documented). If a FCBP engages in sexual activity that may result in a pregnancy, she must agree to use, and be able to comply

with, effective contraception** without interruption, 28 days prior to starting IP, during the study therapy (including dose interruptions), and for 12 weeks (approximately 5 times the mean terminal half-life of luspatercept based on multiple-dose pharmacokinetics [PK] data) after discontinuation of study therapy.

10. Male subjects must:

- a. Practice true abstinence* (which must be reviewed on a monthly basis) or agree to use a condom during sexual contact with a pregnant female or a female of childbearing potential** while participating in the study, during dose interruptions and for at least 12 weeks (approximately 5 times the mean terminal half-life of luspatercept based on multiple-dose PK data) following IP discontinuation, even if he has undergone a successful vasectomy

* True abstinence is acceptable when it is in line with the preferred and usual lifestyle of the subject. [Periodic abstinence (eg, calendar, ovulation, symptothermal, post-ovulation methods) and withdrawal are not acceptable methods of contraception.]

** Agreement to use highly effective methods of contraception that alone or in combination resulting in a failure rate of a Pearl index of less than 1% per year when used consistently and correctly throughout the course of the study. Such methods include: Combined (estrogen and progestogen containing) hormonal contraception: Oral; Intravaginal; Transdermal; Progestogen-only hormonal contraception associated with inhibition of ovulation: Oral; Injectable hormonal contraception; Implantable hormonal contraception; Placement of an intrauterine device (IUD); Placement of an intrauterine hormone-releasing system (IUS); Bilateral tubal occlusion; Vasectomized partner; Sexual Abstinence.

4.3. Exclusion Criteria

The presence of any of the following will exclude a subject from enrollment:

1. Subject has any significant medical condition, laboratory abnormality, or psychiatric illness that would prevent the subject from participating in the study.
2. Subject has any condition including the presence of laboratory abnormalities, which places the subject at unacceptable risk if he/she were to participate in the study.
3. Subject has any condition that confounds the ability to interpret data from the study.
4. Subject has a diagnosis of hemoglobin S/ β -thalassemia or alpha (α)-thalassemia (eg, Hemoglobin H).
5. Subject has active hepatitis C (HCV) infection as demonstrated by a positive HCV-RNA test of sufficient sensitivity, or active infectious hepatitis B as demonstrated by the presence of hepatitis B surface antigen (HBsAG) and/or hepatitis B virus DNA (HBV-DNA) positive, or known positive human immunodeficiency virus (HIV).

Note: Subjects receiving antiviral therapies should have 2 negative HCV-RNA test 3 months apart before ICF signature, ie, one test at the end of the anti-viral therapy and second test 3 months following the first test.

6. Subject had deep vein thrombosis (DVT) or stroke requiring medical intervention \leq 24 weeks prior to randomization.
7. Subjects on chronic anticoagulant therapy are excluded, unless they stopped the treatment at least 28 days prior to randomization. Anticoagulant therapies for prophylaxis and for

- surgery or high-risk procedures as well as low molecular weight (LMW) heparin for superficial vein thrombosis (SVT) and chronic aspirin are allowed before and during the study.
8. Subject has received treatment with another investigational drug or device ≤ 28 days prior to randomization.
 9. Subject had prior exposure to sotatercept (ACE-011) or luspatercept (ACE-536).
 10. Subject has platelet count $> 1000 \times 10^9/L$.
 11. Subjects on iron chelation therapy (ICT) at the time of ICF signature must have initiated the treatment with ICT at least 24 weeks before the predicted randomization date. ICT can be initiated at any time during treatment and should be used according to the label.
 12. Subject had Hydroxyurea and ESA treatment ≤ 24 weeks prior to randomization, and no prior gene therapy.
 13. Subject is pregnant or a lactating female.
 14. Subject has uncontrolled hypertension. Controlled hypertension for this protocol is considered \leq Grade 1 according to National Cancer Institute Common Terminology for Adverse Events (NCI CTCAE) version 4.0 (current active minor version).
 15. Subject has major organ damage, including:
 - a. Liver disease with alanine aminotransferase (ALT) > 3 x upper limit of normal (ULN) or history/evidence of cirrhosis, as well as presence of liver solid masses/tumor detected by ultrasound at screening.
 - b. Heart disease, heart failure as classified by the New York Heart Association (NYHA) classification 3 or higher, or significant arrhythmia requiring treatment, or recent myocardial infarction (MI) within 6 months of randomization.
 - c. Severe lung disease, including pulmonary fibrosis or pulmonary hypertension, ie, \geq G3 NCI CTCAE version 4.0 (current active minor version).
 - d. Estimated glomerular filtration rate (eGFR) < 60 ml/min/1.73 m² (per Modification of Diet in Renal Disease [MDRD] formula).
 16. Subject has received chronic systemic glucocorticoids ≤ 12 weeks prior to randomization (physiologic replacement therapy for adrenal insufficiency is allowed).
 17. Subject had major surgery ≤ 12 weeks prior to randomization (subjects must have completely recovered from any previous surgery prior to randomization).
 18. Subject has history of severe allergic or anaphylactic reactions or hypersensitivity to recombinant proteins or excipients in the investigational product (see Investigator Brochure).
 19. Subject has received immunosuppressants ≤ 28 days prior to randomization.
 20. Subject has history or current malignancies (solid tumors and hematological malignancies) unless the subject has been free of the disease (including completion of any active or adjuvant treatment for prior malignancy) for ≥ 5 years. However, subjects with the following history/concurrent conditions are allowed:

- Basal or squamous cell carcinoma of the skin
- Carcinoma in situ of the cervix
- Carcinoma in situ of the breast
- Incidental histologic finding of prostate cancer (T1a or T1b using the tumor, nodes, metastasis [TNM] clinical staging system)

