3.1.1. Screening Period

Upon giving written informed consent, the subject enters the Screening Period to determine eligibility. A subject identification document (ID) number will be allocated via the Interactive Response Technology (IRT) system as detailed in [Section 7.3](#). The Screening Period will last up to 4 weeks with an administrative window of + 3 days to allow all laboratory results to be available at site for evaluating the subject's eligibility. During the Screening Period, the subject will undergo safety and other assessments to determine eligibility for the study as detailed in [Table 3](#), Table of Events.

If the subject received transfusions during the 24 weeks prior to randomization, 24 weeks of transfusion history (including units or volume transfused and pre-transfusion hemoglobin level), should be recorded in the subject's electronic case report form (eCRF). If subjects received ICT during the 24 weeks prior to randomization, 24 weeks of ICT use history (including types of ICT and doses) should be recorded in the subject's electronic case report form (eCRF).

Re-screening is allowed, and a new subject ID number will be assigned (see [Section 6.1](#)).

Subjects will be stratified at the time of randomization based on:

1. Baseline hemoglobin level:
 - ≥ 8.5 g/dL
 - < 8.5 g/dL
2. Baseline NTDT-PRO T/W score:
 - ≥ 3 points
 - < 3 points

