6.1. Screening Period

Screening evaluations will be performed for all subjects to determine study eligibility. These evaluations must be completed within 4 weeks (+ 3 days administrative window to allow all laboratory results to be available) of randomization via IRT. Two visits should occur at Week -4 and at Week -3 or Week -2 of the screening period, respectively. Hemoglobin levels and other laboratory results assessed by central laboratory must be available on time for evaluating the subject’s eligibility (refer to Table of Events, Table 3 for further information). Dose 1 Day 1 should be scheduled within 3 days of randomization via IRT (it can be on the same day as randomization).

Waivers to the protocol will not be granted during the conduct of this trial, under any circumstances.

Screening laboratory values must demonstrate subject eligibility, but may be repeated within the screening window, if necessary, or subjects can be rescreened (see Section 6.1.1).

The following will be performed at Screening as specified in the Table of Events (Table 3), after informed consent has been obtained:

- Assessment of inclusion/exclusion criteria for study eligibility
- Demographics (date of birth, sex, race, and ethnicity [if allowed by local regulations])

- Complete medical history: specific information regarding all diagnosed relevant medical conditions (occurring prior to screening) should be recorded including any additional details, as needed.
- β -thalassemia comorbidities assessment for NTDT severity score system
- β -thalassemia genotype (ie, beta and alpha globin mutations should be assessed only if not already available)
- Hepatitis B and hepatitis C (HCV-RNA and HBsAG and/or HBV-DNA) should be done only if not done already within 10 weeks before ICF signature)
- Type of iron chelating therapy and period of treatment should be recorded in the related eCRF, at least 24 weeks of history before Dose 1 Day 1 in DBTP.
- Prior medications/therapies: including those taken ≤ 28 days before screening, such as surgery, radiation, systemic or any other therapy for the subject's disease. Prior ESA history (24 weeks prior to randomization) should also be recorded.
- Prior procedures (including all procedures occurring ≤ 28 days before Screening)

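### Exclusion 12 is wrong as written: prior gene therapy never meets it, and read literally it excludes only subjects who had both hydroxyurea and an ESA

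*Protocol*

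**What the plan says.** The list in Protocol Section 4.3 opens with its operating rule: "The presence of any of the following will exclude a subject from enrollment". Number 12 in that list is "Subject had Hydroxyurea and ESA treatment ≤ 24 weeks prior to randomization, and no prior gene therapy". No other visible criterion names hydroxyurea, ESA or gene therapy.

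Protocol Section 6.1 sets what is collected at screening. General prior treatment is requested as "Prior medications/therapies: including those taken ≤ 28 days before screening, such as surgery, radiation, systemic or any other therapy", and one treatment gets its own longer look-back: "Prior ESA history (24 weeks prior to randomization) should also be recorded". Hydroxyurea and gene therapy are not named there. The same section states "Waivers to the protocol will not be granted during the conduct of this trial, under any circumstances", and Section 7.3 requires the sponsor or its representative to acknowledge eligibility before assignment.

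Number 12 is used a second time. Protocol Sections 3.1.3 and 6.3, and SAP Section 4.1.3, include it among the criteria rechecked before subjects who stopped placebo and are in follow-up may enter the open-label phase.

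**The concern.** An exclusion list works only if each entry describes something that bars entry. Number 12 ends with a clause describing something a subject should *not* have had, so its polarity is reversed. Its first half joins two treatments with *and*, although neighbouring entries (numbers 6, 8 and 9) join alternatives with *or*. With waivers barred, sites and the sponsor have to work from this text, and two sites could apply it differently.

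The statistical stake is the baseline. Response is a rise of at least 1.0 g/dL over a baseline averaged from measurements in the 4 weeks before Dose 1 (Protocol Section 9.6.1; SAP Section 10.2). If recent hydroxyurea or ESA use can still be moving hemoglobin at that point, which is an assumption here because the visible documents do not explain the 24-week window, the baseline is unsettled for that subject. The usual safeguard may also miss such a subject. The per-protocol population removes important protocol deviations (SAP Section 5.2.2), and SAP Section 7 defines these as departures from the approved protocol. A hydroxyurea-only subject has not departed from number 12 as literally worded.

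**Working it through.** The plan gives no figure on this point to reproduce. Two checks apply.

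**1. Truth table for number 12.** Write HU, ESA and GT for hydroxyurea within the window, ESA within the window, and any prior gene therapy. Three rules are compared:

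- Literal: HU *and* ESA *and not* GT.
- List reading of the first half, gene-therapy clause as written: (HU *or* ESA) *and not* GT.
- Any of the three: HU *or* ESA *or* GT.

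| HU | ESA | GT | Literal | List reading | Any of three |
|---|---|---|---|---|---|
| no | no | no | – | – | – |
| no | no | yes | – | – | excluded |
| no | yes | no | – | excluded | excluded |
| no | yes | yes | – | – | excluded |
| yes | no | no | – | excluded | excluded |
| yes | no | yes | – | – | excluded |
| yes | yes | no | excluded | excluded | excluded |
| yes | yes | yes | – | – | excluded |
| **Total** | | | **1 of 8** | **3 of 8** | **7 of 8** |

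All four rows with GT = yes escape number 12 under both the literal and the list reading. The gene-therapy fault therefore does not depend on how *and* is read. The hydroxyurea-only and ESA-only gap does: it exists on the literal reading and disappears on the list reading, provided there was no gene therapy.

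**2. Look-back arithmetic for hydroxyurea.** Inputs:

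- The window in number 12 is 24 weeks: 24 × 7 = 168 days before randomization.
- The stated general look-back in Section 6.1 is 28 days before screening.
- For screening length S, Section 3.1.1 says "The Screening Period will last up to 4 weeks with an administrative window of + 3 days", so S is at most 28 + 3 = 31 days.

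Days within the explicit look-back = 28 + S, counting every screening day as covered. Days outside it = 168 − (28 + S).

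- S = 0 (a bound only, since two screening hemoglobin values at least a week apart are required): 168 − 28 = 140 days, 20.0 weeks.
- S = 28: 168 − 56 = 112 days, 16.0 weeks.
- S = 31: 168 − 59 = 109 days, 15.6 weeks.

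After a full screening period, about 16 of the 24 weeks have no explicit hydroxyurea look-back in visible Section 6.1. For ESA the stated history matches the whole window. This counts days without a named instruction. It does not count days that go unrecorded.

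**The case against.** The best defence is that no careful site would read number 12 as bare logic. The list is not uniform (number 11 is also phrased as a requirement), and the separate 24-week ESA history suggests that ESA was meant to count on its own. There is also a backstop in exclusion 3: "Subject has any condition that confounds the ability to interpret data from the study". Exclusion 8 covers recent investigational products, and the sponsor checks eligibility before assignment. These points stand. Failing to meet number 12 is not the same as entering the trial, and the list reading of *and* is possible. They do not repair the gene-therapy clause, and a discretionary backstop does not replace a stated rule.

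A reader might infer more in three places.

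- *Prior hydroxyurea and gene therapy go unrecorded.* The documents do not support this. The 28-day item in Section 6.1 is introduced as an inclusion, not a limit, and covers therapy for the disease. Complete medical history is taken, and Table 3 has a row for disease-specific prior therapies. The text of Protocol Section 8 and of SAP Section 8.4.1, whose title in the SAP contents covers prior β-thalassemia treatment, is withheld from the public copy.
- *The treatment effect is diluted by a calculable amount.* The documents give no count of affected subjects, so no such figure can be derived. Randomization spreads any such subjects over both arms, and nothing here calls the stated power of at least 99% into question.
- *Affected subjects are already protocol deviations.* On the literal reading they are not, and that is why the intended rule must be written down first.

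It is also true that rewording cannot change who was randomized: SAP Section 16 says enrollment had finished when the pandemic began.

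**Conclusion.** The point holds as a defect in an operative eligibility rule. The reversed polarity of the gene-therapy clause is certain on the text. The hydroxyurea-only and ESA-only gap is the literal reading but not the only one. In terms of the rule, number 12 catches one or three of eight treatment histories, against seven if each treatment was meant to exclude on its own. That last intent is an assumption for the sponsor to confirm.

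On data capture, the supportable statement is narrow: visible Section 6.1 names a 24-week history for ESA, sets no explicit one for hydroxyurea, and does not name gene therapy. The effect on the results cannot be sized from the documents, and there is no sign that it threatens the primary conclusion. The point still has practical use in the open-label recheck and in the blinded deviation review, which SAP Section 7 finalizes before database lock.

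**What to change.** 1. **Number 12.** The sponsor should reconcile the wording with its intent, stating each of the three named treatments as a separate condition with exclusion polarity, for example joined by *or* if that is the intent. Which treatments should bar entry is for the sponsor to state.
2. **Section 6.1.** Align the history items with that rule, so that each treatment named in number 12 has an explicit look-back matching its condition. If a withheld section already does this, a cross-reference is enough.
3. **Open-label recheck.** Apply the corrected wording under Sections 3.1.3 and 6.3. For placebo subjects coming from follow-up, Section 6.3 already collects at least 24 weeks of prior medication. That section also speaks of exclusion criteria being met, which should be reworded at the same time.
4. **Randomized subjects.** Document the intended rule, then review existing records against it, blinded and before database lock. Any subject who does not meet it is then identified for the per-protocol sensitivity analysis already planned in SAP Section 10.

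The cost is one sentence in Section 4.3, one history line, and a limited record review. The per-protocol population may lose a few subjects; the ITT analysis is unchanged.
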